3.8.1.1. Deaths, Serious and Other Significant AEs

The number and percentage of subjects who have serious adverse events (SAE) and AEs leading to discontinuation from the treatment will be summarized by system organ class and preferred term. And the number and percentage of subjects reporting SAEs will be summarized by system organ class, preferred term, and relationship to study drug.

By-subject listings will be provided for SAEs, AEs leading to treatment discontinuation and AEs leading to death.

3.8.1.2. AEs of Special Interest

In addition, incidence of a selected subset of relevant AEs in this class of drugs (eg, TEAE to evaluate potential of movement disorders, TEAE to evaluate potential of suicidal ideation and behavior, etc.) will be summarized by preferred term. The selection of AEs per subset will be based on the preferred terms from Standardized MedDRA queries (SMQs) or Customized MedDRA queries (CMQs).

3.8.2. Clinical Laboratory Parameters

Laboratory parameters will be presented in conventional (ie, US) units. Only scheduled laboratory parameters will be included in the summaries, unless specified otherwise. All laboratory data, including those collected at unscheduled visits, will be included in the listings.

Laboratory results including baseline and change from baseline for the Safety Population during the treatment period for chemistry and hematology parameters will be summarized by visit.

Clinical laboratory test values, scheduled or unscheduled, will be considered potentially clinically significant (PCS) if they meet PCS criteria listed in [Table 3](#). The number and

percentage of subjects who have postbaseline PCS clinical laboratory values will be summarized. The percentages will be calculated based on the number of subjects with abnormal baseline value and have at least one postbaseline assessment. All PCS values including baseline PCS values will be included in supportive listings.

Shift tables for selected fasting metabolic parameters (glucose, total cholesterol, low density lipoprotein [LDL], high density lipoprotein [HDL], triglycerides, and hemoglobin A1c [HbA1c]) and liver function tests will be presented. The criteria are summarized in [Table 4](#), [Table 5](#), and [Table 6](#).

Table 3: Criteria of Potentially Clinically Significant (PCS) Abnormality for Selected Analytes

Parameter	Criteria
Chemistry	
Albumin	<2 g/dL
Alkaline Phosphatase (U/L)	$\geq 3 \times \text{ULN}$
Alanine Aminotransferase (U/L)	$\geq 3 \times \text{ULN}$
Aspartate Aminotransferase (U/L)	$\geq 3 \times \text{ULN}$
Bilirubin, Total	$\geq 2.0 \text{ mg/dL}$
Blood Urea Nitrogen	$>30 \text{ mg/dL}$
Cholesterol, Random	$>400 \text{ mg/dL}$
Cholesterol, Fasting ^a	$\geq 240 \text{ mg/dL}$
Cholesterol, Fasting	Increase $\geq 40 \text{ mg/dL}$
Cholesterol, HDL Fasting	$<40 \text{ mg/dL}$
Cholesterol, HDL Fasting	Decrease $\geq 20 \text{ mg/dL}$
Cholesterol, LDL Fasting	$\geq 160 \text{ mg/dL}$
Cholesterol, LDL Fasting	Increase $\geq 30 \text{ mg/dL}$
Creatine Kinase (U/L)	$\geq 3 \times \text{ULN}$
Creatinine	$\geq 2.0 \text{ mg/dL}$
Glucose, Random	$<40 \text{ mg/dL}$ or $\geq 250 \text{ mg/dL}$
Glucose, Fasting	$<50 \text{ mg/dL}$ or $\geq 126 \text{ mg/dL}$
Glucose, Fasting	Increase $\geq 10 \text{ mg/dL}$
HbA1c	$\geq 5.7\%$
Potassium	$<3 \text{ mmol/L}$ or $>5.5 \text{ mmol/L}$
Lactate Dehydrogenase (U/L)	$>3 \times \text{ULN}$

Parameter	Criteria
Prolactin (Female)	$\geq 1 \times \text{ULN}^b$
Prolactin (Male)	$\geq 1 \times \text{ULN}^b$
Prolactin (Female)	$\geq 3 \times \text{ULN}^b$
Prolactin (Male)	$\geq 3 \times \text{ULN}^b$
Sodium	$<130 \text{ mmol/L}$ or $>150 \text{ mmol/L}$
Triglycerides, Fasting	$\geq 200 \text{ mg/dL}$
Triglycerides, Fasting	Increase $\geq 50 \text{ mg/dL}$
Hematology	
Eosinophils	$>1.0 \times 10^3/\mu\text{L}$
Hematocrit (Female)	$\leq 32\%$
Hematocrit (Male)	$\leq 37\%$
Neutrophils, Absolute	$<1.5 \times 10^3/\mu\text{L}$
Platelets	$<75.0 \times 10^3 \text{ cells}/\mu\text{L}$ or $\geq 700.0 \times 10^3 \text{ cells}/\mu\text{L}$
Leukocytes	$\leq 2.8 \times 10^3/\mu\text{L}$ or $\geq 16.0 \times 10^3/\mu\text{L}$

^a Reported fasting

^b ULN is 30 ng/mL for females and 20 ng/mL for males

Table 4: Shifts Category from Baseline to Any Postbaseline for Selected Lipid Parameters

Total Cholesterol (fasting) mg/dL
Normal (<200) to High (≥ 240)
Borderline (≥ 200 and < 240) to High (≥ 240)
Normal (<200) to Borderline (≥ 200 and < 240)
LDL Cholesterol (fasting) mg/dL
Normal (<100) to High (≥ 160)
Borderline (≥ 100 and < 160) to High (≥ 160)
Normal (<100) to Borderline (≥ 100 and < 160)
HDL Cholesterol (fasting) mg/dL
Normal (≥ 40) to Low (< 40)
Triglycerides (fasting) mg/dL
Normal (<150) to High (≥ 200)

Borderline (≥ 150 and < 200) to High (≥ 200)
Normal (< 150) to Borderline (≥ 150 and < 200)

Table 5: Shift Category from Baseline to Any Postbaseline in Glucose and HbA1c

Glucose (fasting) mg/dL
Normal (< 100) to Impaired (≥ 100 and < 126)
Normal (< 100) to High (≥ 126)
Impaired (≥ 100 and < 126) to High (≥ 126)
HbA1c %
Normal ($< 5.7\%$) to Borderline ($\geq 5.7\%$ and $< 6.5\%$)
Borderline ($\geq 5.7\%$ and $< 6.5\%$) to High ($\geq 6.5\%$)
Normal ($< 5.7\%$) to High ($\geq 6.5\%$)

Table 6: Shift Category from Baseline to Any Postbaseline in Liver Function Test

Alanine Aminotransferase (ALT) (U/L)
Shift from Normal to $\geq 3 \times$ ULN
Shift from Normal to $\geq 5 \times$ ULN
Shift from Normal to $\geq 10 \times$ ULN
Aspartate Aminotransferase (AST) (U/L)
Shift from Normal to $\geq 3 \times$ ULN
Shift from Normal to $\geq 5 \times$ ULN
Shift from Normal to $\geq 10 \times$ ULN
Bilirubin, Total (mg/dL)
Shift from Normal to $> 1 \times$ ULN
Shift from Normal to $\geq 2 \times$ ULN

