8.3.9.2. Hematology, Biochemistry, and Urinalysis

Blood and urine samples for laboratory assessments will be collected at the timepoints specified in Table 3. Specific hematology, biochemistry, and urinalysis assessments are listed in Table 4. Subjects will be instructed not to eat or drink anything (except water) for 8 hours before each visit where blood samples for biochemistry and hematology assessments will be collected. Samples will be collected in accordance with the site's usual procedures and analyzed by a central laboratory. Laboratory assessments may be repeated at the Investigator's discretion.

Table 4: Clinical Laboratory Assessments

| Hematology | Biochemistry | Urinalysis |
|-----------------------------------|-----------------------------|-------------------------------|
| Hematocrit | General Chemistry | Bilirubin |
| Hemoglobin | Albumin | Color and appearance |
| Platelets | Bicarbonate | Glucose |
| Red blood cell count | Calcium | Ketones |
| Total and differential (absolute) | Chloride | Leukocytes |
| white blood cell count | Creatine phosphokinase | Nitrite |
| | Glucose | Occult blood |
| | Lactic dehydrogenase | рН |
| | Potassium | Protein |
| | Sodium | Specific gravity |
| | Total protein | Urobilinogen |
| | Uric acid | Cotinine |
| | Endocrine Function Test | Microscopic examination of |
| | HbA1c | sediment, only if urinalysis |
| | Prolactin | dipstick results are abnormal |
| | Insulin | |
| | Liver Function Tests | |
| | Alanine aminotransferase | |
| | Alkaline phosphatase | |
| | Aspartate aminotransferase | |
| | Gamma-glutamyl transferase | |
| | Total bilirubin | |
| | Renal Function Tests | |
| | Blood urea nitrogen | |
| | Creatinine | |
| | Lipid Panel | |
| | High-density lipoprotein | |
| | Low-density lipoprotein | |
| | Total cholesterol | |
| | Triglycerides | |

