7. GENERAL STATISTICAL METHODOLOGY (AND REPORTING OF RESULTS)

In general, summary statistics (n, mean, SD, median, minimum, and maximum for continuous variables, and number and percentage of subjects in each category for categorical variables) will be provided. All summary tables will be based on observed data, and missing values will not be imputed, unless otherwise indicated. Measurements collected from unscheduled visits or repeated assessments will not be included in the by-visit summary tables or figures but will be included in the analyses for the PCS postbaseline values, and subject listings. Source data for the summary tables will be presented as subject data listings.

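### Read literally, the SAP keeps unscheduled, repeat and unmapped early-termination values out of the any-postbaseline laboratory shift tables, so counts at the highest ALT/AST and HbA1c levels may be understated

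*SAP*

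**What the plan says.** SAP 3.8.2 opens with a rule for laboratory data: "Only scheduled laboratory parameters will be included in the summaries, unless specified otherwise". It then makes one exception: "Clinical laboratory test values, scheduled or unscheduled, will be considered potentially clinically significant (PCS) if they meet PCS criteria listed in" SAP Table 3. The next paragraph introduces the shift tables for metabolic parameters and liver tests (Tables 4 to 6) and does not mention unscheduled values. The title of Table 6 reads "Shift Category from Baseline to Any Postbaseline in Liver Function Test"; Tables 4 and 5 use the same any-postbaseline wording.

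SAP 7 keeps unscheduled and repeat measurements out of by-visit tables and figures, but says they "will be included in the analyses for the PCS postbaseline values, and subject listings". SAP 6.1 also bars unscheduled visits from by-visit statistics. It allows an ET value to fill an empty scheduled visit; an ET visit that cannot be mapped goes to the listing and not to tables or figures.

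Protocol Table 3 schedules biochemistry and hematology at quarterly visits and at EOT/ET. Unscheduled values arise because protocol 8.3.9.2 states: "Laboratory assessments may be repeated at the" investigator's discretion.

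**The concern.** An any-postbaseline shift table is meant to show the worst level each subject reached. If its input is limited to scheduled and mapped samples, a higher value recorded at a repeat test, or at an ET visit whose slot is taken, is in the database but not in the table.

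Safety is part of the primary objective, and protocol 5.5 lists abnormal liver function tests among the most common adverse events seen with the product. The ≥5× and ≥10× ULN levels for ALT and AST are tabulated only in Table 6. HbA1c ≥6.5%, which protocol 7.3 ties to discontinuation at any time, is tabulated only in Table 5. These are the counts a safety reader would look for first. Two programmers working from the same SAP could also produce different versions of them.

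**Working it through.** The plan gives no figure to reproduce here. The check is on the text, followed by the direction of the effect.

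**1. Which rule governs Tables 4 to 6?**
- SAP 3.8.2: the scheduled-only rule covers laboratory summaries in general, not only by-visit ones. Its one exception is PCS.
- SAP 7: excludes unscheduled and repeat values from by-visit output and adds them to PCS analyses and listings. The shift tables are in neither group.
- SAP 6.1: excludes unscheduled visits from by-visit statistics. Its sentence on unmapped ET visits is not limited to by-visit output.
- Titles of Tables 4 to 6: any postbaseline value.

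No sentence admits unscheduled values to the shift tables, so the 3.8.2 default applies on a literal reading. The titles conflict with it.

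**2. Where is the PCS table a backstop?** Comparing the top shift levels with SAP Table 3:

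| Parameter | Top shift level | PCS row | Matched? |
|---|---|---|---|
| Fasting glucose | ≥126 mg/dL | ≥126 | Yes |
| Fasting total cholesterol | ≥240 mg/dL | ≥240 | Yes |
| Fasting LDL | ≥160 mg/dL | ≥160 | Yes |
| Fasting HDL | <40 mg/dL | <40 | Yes |
| Fasting triglycerides | ≥200 mg/dL | ≥200 | Yes |
| ALT, AST | ≥3× ULN | ≥3× ULN | Yes |
| ALT, AST | ≥5× and ≥10× ULN | none | **No** |
| HbA1c | ≥6.5% | ≥5.7% only | **No** |

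Total bilirubin is given in multiples of ULN in Table 6 and in mg/dL in Table 3. Without the laboratory's ULN the two cannot be matched, so it is left aside.

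**3. Direction.** For subject i, let S be the scheduled and mapped postbaseline values and U the unscheduled, repeat and unmapped ET values. For a high threshold c, among subjects eligible at baseline:
- literal count = number with max(S) ≥ c
- full count = number with max(S and U together) ≥ c
- full minus literal = number with max(U) ≥ c and max(S) < c, which is ≥ 0

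The literal count is therefore equal or lower, never higher. This holds for the top levels only. Intermediate categories, such as normal to borderline HbA1c, can move either way as subjects pass into the top one.

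**4. When is an ET value lost?** In SAP Table 11, Visit 7 has target Day 169 and window [127, 210]; Visit 10 has target Day 253 and window [211, 294]. Take a subject sampled on Day 169 who then stops:
- ET on Days 170 to 210 (210 − 170 + 1 = 41 days): the Visit 7 slot is filled, so the value is listed only.
- ET on Days 211 to 252 (252 − 211 + 1 = 42 days): the value maps to Visit 10.

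With on-target visits, an ET value in about half of the interval between two quarterly visits (41 of 83 days) cannot be mapped.

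**5. Size.** The difference in step 3 needs the number of subjects whose unscheduled or unmapped value crossed a threshold that no scheduled or mapped value reached. The documents give no liver-event rate, no frequency of repeat tests and no duration of excursions, so no figure can be derived.

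**The case against.** The strongest reply is that exclusion is inferred. The 3.8.2 rule yields where something else is specified, and a title promising any postbaseline value can be read as doing that. SAP 6.1 and 7 bar unscheduled values only from by-visit output, which Tables 4 to 6 are not. Programming specifications and table shells are separate documents and may settle it. This stands in part: exclusion is the literal default and conflicts with the titles, but it is not written expressly for these tables.

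It is also fair that nothing disappears from the record. All laboratory data are listed, and out-of-range values judged clinically significant are recorded as adverse events (protocol 13.2). PCS counts include unscheduled values, which covers the matched rows above. That cover is weaker than it looks, because PCS percentages are based on subjects with an abnormal baseline while Table 6 starts from normal. That is a separate defect.

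A reader might go further than the documents allow in three ways:
- That only quarterly samples count. EOT/ET samples are scheduled too, and ET values can be mapped.
- That peaks usually fall at unscheduled tests. Protocol 8.3.9.2 says only that tests may be repeated.
- That the 84-day spacing gives the loss. If an excursion is assumed to last 14 to 28 days, a quarterly draw misses it with probability 1 − 14/84 = 83% to 1 − 28/84 = 67%. That is a chance of missing an excursion under an assumed duration. It is not the shortfall, which counts only peaks that an unscheduled or unmapped ET sample actually recorded.

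**Conclusion.** The point holds as a conflict between the laboratory default and the table titles, with a known direction of risk. Applied literally, SAP 3.8.2 and 6.1 can lower the counts of ALT/AST ≥5× and ≥10× ULN and of HbA1c ≥6.5%, or leave them unchanged. They cannot raise them. The matched glucose and lipid cut-offs, and ALT/AST ≥3× ULN, are less exposed because PCS admits unscheduled values.

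The documents do not support saying that the counts are understated. The shortfall may be zero, and would be if no unscheduled, repeat or unmapped ET value crossed one of these thresholds ahead of every scheduled or mapped value. The conclusion rests on reading 3.8.2 as covering the shift tables. If the unseen programming specifications already use all values, the SAP text still needs correcting. The analyses are descriptive, so no test or stated figure changes.

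**What to change.** State in SAP 3.8.2 that Tables 4 to 6 use each subject's worst postbaseline value in the treatment period from all samples: scheduled, unscheduled or repeat, and ET whether mapped or not. For fasting parameters, use only samples reported as fasting. Repeat the exception in SAP 7 beside the one for PCS, and in SAP 6.1 so that the sentence on unmapped ET visits does not override it. By-visit summaries stay on scheduled samples.

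The cost is a short text change in three places and a changed record filter for three tables, with no new data collection. The top-level shift counts may come out slightly less favourable.

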5.5. Benefit-Risk Assessment

As stated in the background section, first- and early-episode schizophrenia and bipolar I disorder are critical phases of the diseases, where optimal antipsychotic efficacy is crucial. Treatment with ALKS 3831 combines the advantages of the antipsychotic efficacy of olanzapine in treating both schizophrenia and bipolar disorder, with the potential to mitigate the known effect of olanzapine treatment of excessive weight gain. The antipsychotic efficacy seen in stable subjects treated in study ALK3831-302 was similar between ALKS 3831 and olanzapine as measured by Total PANSS and CGI scores. Based on the available data from the completed studies in healthy volunteers (ALK33-301) and in subjects with schizophrenia (ALK3831-302), subjects treated with ALKS 3831 have been shown to gain less weight compared to subjects treated with olanzapine alone. In ALK3831-302, the prevention of weight gain persisted during the 3 month ALKS 3831 treatment period.

The important identified risks associated with the use of olanzapine include weight gain, glucose dysregulation, and dyslipidemia. For additional information on the known risks of olanzapine, see the local label. The safety profile of ALKS 3831 is consistent with that of olanzapine (see local label). In study ALK3831-302, the only adverse events reported with ALKS 3831 treatment occurring in ≥5% of subjects and at ≥2 times the rate of olanzapine alone were somnolence, sedation, dizziness, and constipation. Notably, these are all labeled events for olanzapine. The most common adverse events noted in clinical studies in >2% of subjects with ALKS 3831 to date have been somnolence, dizziness, weight increased, sedation, increased appetite, headache, orthostatic hypotension, and liver function test abnormal (see current ALKS 3831 Investigator's Brochure). In summary, data from the completed ALKS 3831 studies have demonstrated a favorable benefit-risk profile for further investigating ALKS 3831 in subjects with schizophrenia, schizophreniform disorder, or bipolar I disorder.

6. **OBJECTIVES**

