2. SAMPLE SIZE CONSIDERATION

No formal sample size calculation is performed for this extension study. A sample size of approximately 500 is based on the estimated maximum number of subjects who might be expected to continue from the antecedent Phase 3 studies within 7 days (ALK3831-A304, ALK3831-A306, or ALK3831-A307).

3. DATA ANALYSIS**3.1. General Statistical Methodology**

Baseline for efficacy or safety analyses is defined as the last non-missing assessment before the first dose of ALKS 3831 in the ALK3831-A308 study, and it will be used for all efficacy and safety analyses, unless specified otherwise.

All results from this analysis will be presented for the overall group, ie all subjects as a single group, and not by previous treatment sequence in antecedent studies of ALK3831-A303 and ALK3831-A305.

In general, descriptive statistics: n, mean, standard deviation (SD), median, minimum, and maximum, for continuous variables and number and percentage of subjects in each category for categorical variables will be provided.

All source data will be presented as subject data listings.

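### SAP Table 6 counts ALT and AST elevations of ≥5× and ≥10× ULN only from a normal baseline, so subjects who enter A308 with raised enzymes have no separate count at those levels

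*SAP*

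**What the plan says.** Four parts of the plan bear on this point.

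- **Shift table.** SAP Section 3.8.2 plans "Table 6: Shift Category from Baseline to Any Postbaseline in Liver Function Test". For ALT and for AST it has three rows, at 3, 5 and 10 times ULN, all starting from normal. The upper two read "Shift from Normal to $\geq 5 \times$ ULN" and "Shift from Normal to $\geq 10 \times$ ULN". The bilirubin rows also start from normal.
- **PCS table.** "Table 3: Criteria of Potentially Clinically Significant (PCS) Abnormality for Selected Analytes" has one level each for ALT and AST, ≥3× ULN. The plan is that the number and "percentage of subjects who have postbaseline PCS clinical laboratory values will be summarized", using scheduled and unscheduled values. On the denominator it says: "The percentages will be calculated based on the number of subjects with abnormal baseline value and have at least one postbaseline assessment". All PCS values are listed.
- **Baseline.** SAP Section 3.1: "Baseline for efficacy or safety analyses is defined as the last non-missing assessment before the first dose of ALKS 3831" in A308. Protocol Table 3 schedules no biochemistry at Visit 1, so this value will usually come from the antecedent study, after treatment there.
- **Who may enter.** Protocol Sections 7.1 and 7.2 set no ALT or AST limit of their own for A308. Protocol Section 5.5 ends its list of the most common adverse events with ALKS 3831, each seen in more than 2% of subjects, with "orthostatic hypotension, and liver function test abnormal".

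**The concern.** A subject whose transaminases rose during the antecedent study carries that rise into A308 as baseline and then falls outside every row of Table 6. If the enzymes climb further, no count shows how far. Tables 4 and 5 of the same SAP treat other analytes differently: for total cholesterol, LDL, triglycerides, glucose and HbA1c they include shifts from borderline or impaired baselines. Only the liver tests and the two-category HDL entry are restricted to normal starters.

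Long-term safety is part of the primary objective. A reader who takes the ≥5× and ≥10× rows as the study's picture of marked transaminase elevation would be looking at normal-baseline subjects only.

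**Working it through.** The plan states no figure on this point, so there is none to reproduce. The check has two steps.

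**1. Where each kind of subject is counted.** Apply the Table 6 rows and the Table 3 criterion to three example peaks of ALT or AST.

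| Baseline | Peak (× ULN) | Table 6 rows entered | Meets Table 3 criterion (≥3×) |
|---|---|---|---|
| Normal | 3.5 | ≥3 | yes |
| Normal | 6 | ≥3, ≥5 | yes |
| Normal | 12 | ≥3, ≥5, ≥10 | yes |
| Raised | 3.5 | none | yes |
| Raised | 6 | none | yes |
| Raised | 12 | none | yes |

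The last three lines are identical. For raised-baseline subjects, no planned count separates a peak of 12× from one of 3.5×.

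**2. How many cases this could involve.** Let *s* be the share of subjects with a raised baseline, and RR their risk of reaching ≥5× ULN relative to normal-baseline subjects. The share of all ≥5× cases that Table 6 leaves out is

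share = s × RR / (s × RR + 1 − s).

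At RR = 1 this reduces to *s*. The documents give neither *s* nor RR, so what follows is illustration only. Assume N = 500 (the planned number), a ≥5× risk of 0.5% from a normal baseline, and the values below for the rest. Each cell gives the expected number of ≥5× cases left out, N × s × risk, and their share of all ≥5× cases.

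| *s* | Expected ≥5× from normal baseline | Raised-baseline risk 0.5% (RR = 1) | 1% | 3% | 5% |
|---|---|---|---|---|---|
| 5% (25 subjects) | 475 × 0.005 = 2.375 | 0.125 (5%) | 0.25 (10%) | 0.75 (24%) | 1.25 (34%) |
| 10% (50) | 450 × 0.005 = 2.25 | 0.25 (10%) | 0.5 (18%) | 1.5 (40%) | 2.5 (53%) |
| 20% (100) | 400 × 0.005 = 2.0 | 0.5 (20%) | 1.0 (33%) | 3.0 (60%) | 5.0 (71%) |

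For example, with *s* = 20% and a 5% risk, 100 × 0.05 = 5.0 and 5.0 / (2.0 + 5.0) = 71%. Across these assumptions the shares run from 5% to 71%, but the absolute numbers are small: from well under one subject to about five.

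**The case against.** A reader might infer that severe elevations in raised-baseline subjects are tabulated nowhere. The documents do not support that.

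- Table 3 counts any postbaseline ALT or AST of ≥3× ULN, with no normal-baseline condition on the value. Its percentage, as written, is based on abnormal-baseline subjects, the very group at issue.
- All PCS values and all laboratory data are listed.
- By-visit chemistry summaries cover the whole Safety Population and include the maximum.
- Under Protocol Section 13.2, out-of-range values judged clinically significant become adverse events, and SAP Section 3.8.1 tabulates treatment-emergent events by severity.

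A reader might also infer that the Table 6 counts are wrong. They are not: it is labelled as a shift table and counts shifts from normal correctly. Nor does the adverse event frequency in Protocol Section 5.5 give the prevalence of raised enzymes at A308 baseline.

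All of this stands, but none of it supplies the missing grading. Table 3 has one level. A listing is not a count. By-visit summaries leave out unscheduled values and are not expressed in multiples of ULN. Severity under Protocol Section 13.5 is graded by interference with usual activities, so an asymptomatic 12× value could be recorded as mild. The event queries in SAP Appendices 1 to 5 include no hepatic one.

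The abnormal-baseline denominator is itself questionable, since the weight PCS analysis uses all subjects with a postbaseline value. That is a separate matter. If it were changed to normal-baseline subjects only, however, the raised-baseline group could lose its ≥3× count as well.

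**Conclusion.** The point holds in a limited form. For subjects who enter A308 with raised ALT or AST, elevations of ≥5× and ≥10× ULN are not tabulated separately. They appear within the ≥3× PCS category, in listings and, where judged clinically significant, as adverse events graded by the investigator.

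The size of the gap is unknown. The one general statement is that, at equal risk, the share of ≥5× cases left out equals the share of subjects with a raised baseline; it is larger if those subjects are at higher risk, which the documents neither state nor exclude. The raised-baseline group need not be empty, because A308 sets no enzyme limit of its own and baseline follows treatment in an antecedent study. Its size would also depend on the antecedent studies' criteria and on investigator judgement at entry.

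The study is single-arm and descriptive, with no test or decision tied to Table 6, and no data are lost. This is a worthwhile, inexpensive improvement to the hepatic safety reporting, and it invalidates no planned result.

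**What to change.** In Table 6, tabulate maximum postbaseline ALT and AST at ≥3×, ≥5× and ≥10× ULN for all Safety Population subjects with a postbaseline value, split by baseline normal and above normal. The present rows become the normal-baseline stratum, so nothing planned is lost. State the denominator of each stratum, and state that unscheduled values count, as they already do for PCS values.

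Optionally, and as a separate addition, give a count and listing of subjects with ALT or AST ≥3× ULN and total bilirubin ≥2× ULN at the same visit. Transaminases and bilirubin are now tabulated apart, and no planned table shows both raised together.

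The cost is a change of SAP wording and one re-specified table, with no new data and no change to study conduct. The reported counts of marked elevations may rise slightly.
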